12.1 Primary efficacy variables

The primary efficacy variable is the response rate based on the Cheson criteria. The response rate will be presented in percentages together with 95 % confidence interval (CI) calculated using the Wilson score method.

The analysis will be conducted both for the overall population and separately by the dosing schedule.

The response rate will also be presented in several subgroups, if feasible. Following subgroups will be investigated for the primary endpoint: primary vs. secondary AML, remission >12 Months vs. remission <12 months, relapse after SCT vs. no prior SCT, karyotypic risk group, FLT3 vs. NPM1 mutation.

12.2 Secondary efficacy variables

The secondary efficacy variables; rate of partial remissions, percentage of patients being transplanted after induction therapy and early death rate will be analysed using similar methods as with the primary analysis.

Overall survival, recurrence-free-survival and event-free survival will be analysed applying the Kaplan-Meier-method (KM). OS is calculated from the date of informed consent to the date of death, the patients still alive will be censored at the last date of follow-up. RFS is calculated from the date of informed consent to the date of recurrence or death, whichever occurs first, censoring patients who were alive without recurrence on the date of last follow-up visit. EFS is calculated from the date of CR/CRi until death or relapse, whichever occurs first. Patients are censored on the date of last follow-up visit if they are alive without relapse.

The survival curves will be displayed graphically for the overall population and by dosage schedule. In addition median survival and follow-up times (including interquartile range and 95 % CI if feasible) will be calculated.

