3 STUDY DESIGN

3.1 Overview of Study Design and Dosing Regimen

This is a multi center, open-label, non-randomized phase II trial study.

Patients are informed, screened and enrolled in the study at the time of progression of disease on prior chemotherapy documented by Bone Marrow Aspirate. Treatment should start within two weeks after enrolment.

The study design is displayed in Figure 1.

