5.2 Study Procedures

The Schedule of Study Events is displayed in tabular form as Table 2.

Table 2: Schedule of Assessments during the study

Assessments by Visit	Screening	Baseline	Induction cycle(s)		Consolidation (if applicable)	Maintenance (if applicable)	End of treatment	Follow-up ¹⁹
Time window	Within 14 days prior to registration	After registration, before Day1 of induction	During Treatment Twice weekly	End of Cycles	weekly (D2,8,15,21 ± 2 days)	Twice per cycle D1,15 ± 2 days)	30-days after last dose/prior to SCT	Every 3 months ± 28 days
Informed consent ¹	X							
Inclusion and exclusion criteria	X							
Demographics	X							
Medical history ²	X							
Pregnancy test (if applicable) ³	X							
Physical examination and ECOG ⁴	X		X	X	X	X	X	
Body height and weight ⁵	X			X	X	X	X	
BSA	X							
Vital signs ⁶	X		X	X	X	X	X	
Standard clinical neurologic examination	X							
12-lead ECG	X			X	X	X		
Cardiac ultrasound ⁷	X			X			X	
Hematology ⁸	X		X	X	X	X	X	X
Hematological Recovery status ²¹			X ²¹	X ²¹	X ²¹	X ²¹	X ²¹	X ²¹

Assessments by Visit	Screening	Baseline	Induction cycle(s)		Consolidation (if applicable)	Maintenance (if applicable)	End of treatment	Follow-up ¹⁹
Calculation ⁹ (or measurement) of GFR	X			X	X		X	
Clinical Chemistry ¹⁰	X			X	X	X	X	
Urine analysis ¹¹	X			X	X ¹¹	X ¹¹		
Coagulation test ¹²	X		X	X	X ¹²	X ¹²		
HIV testing ¹³	X							
Assessment of signs and symptoms, AE	X		X	X	X		X	
CTCAE v 4.03 scale toxicity			X	X	X	X	X	
Concomitant medication	X		X	X	X	X	X	
Bone Marrow Aspirate ¹⁴	X			X	X	X ¹⁴		X ¹⁴
Survival								X
Selinexor baseline dose ¹⁵		X						
Bone Marrow aspirates for translational research ¹⁶ (optional)		X						
Blood draws for translational research ¹⁷ (optional)			X		X			
Blood draws for Pharmacokinetics ¹⁸ (optional)			X					
Ophthalmological examination ²⁰	X							

Notes

¹ Prior to the first study-specific measures

² Medical history includes baseline symptoms as well as a detailed history of prior cancer therapies including start and stop dates, response of prior cancer therapies, disease progression during or after therapy, as well as discontinuations due to intolerance or any other serious illness.

³ Applicable for women of childbearing potential. Serum β-HCG test within 7 days before the first dose of study drug. To be repeated by urine test, if date of first result exceeds the 7-day window

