7.1 Intention-to-treat (ITT) set

The ITT set includes all subjects who have received study medication at least once and for whom efficacy data upon treatment are available.

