14.2 Efficacy data

Figure 14.2.1 Kaplan-Meier curves for Overall survival (ITT)

Figure 14.2.2 Kaplan-Meier curves for Recurrence-free survival (ITT)

Figure 14.2.3 Kaplan-Meier curves for Event-free survival (ITT)

Figure 14.2.4 Kaplan-Meier curves for Overall survival (censoring at time of SCT) (ITT)

Figure 14.2.5 Kaplan-Meier curves for Recurrence-free survival (censoring at time of SCT) (ITT)

Figure 14.2.6 Kaplan-Meier curves for Event-free survival (censoring at time of SCT) (ITT)

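### OS and RFS are timed from informed consent in a set that admits only patients later dosed, so usually up to about two weeks of survival is guaranteed

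*SAP*

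**What the plan says.** On the clock, SAP 12.2 says that "OS is calculated from the date of informed consent to the date of death" and that "RFS is calculated from the date of informed consent to the date of recurrence or death, whichever occurs first". The protocol gives no OS start date.

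On the set, SAP 7.1 defines ITT as "all subjects who have received study medication at least once and for whom efficacy data upon treatment are available", and protocol 8.3.1 has the same definition. The table and figure plan in SAP 19.2 puts the OS and RFS curves on ITT. It repeats the summary tables on the PP set, which requires completion of treatment up to Visit 9 (SAP 7.2).

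On the interval between consent and treatment, consent precedes every study-specific procedure (protocol 11.2). The windows are not consistent:

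- Protocol 5.2, Table 2 places screening "Within 14 days prior to registration", and protocol 3.1 adds that "Treatment should start within two weeks after enrolment".
- Protocol 5.2.2 counts the 14-day screening window back from the start of induction instead.
- Protocol 4.1 requires the baseline leukemia assessment within two weeks before treatment.
- Protocol 4.4 puts the first dose within two weeks of the marrow confirming progression.

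SAP 12.3 changes only the censoring at transplant. The 2018 addendum updates the survival data but alters neither the time origin nor the analysis set.

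**The concern.** A patient enters the analysis by an event (a dose, and then efficacy data) that happens after the clock has started. A patient who dies between consent and that event is left out, while every patient who remains is credited with the interval. The plan has no delayed-entry or landmark analysis, and no all-consented or all-registered set, to offset this.

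At stake are the OS and RFS medians and the early part of both curves. The trial has one arm and no internal control, so anyone who sets these estimates beside outside figures will carry the shift along.

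**Working it through.** The documents give no median, hazard or event count for OS or RFS, so there is no planned figure to reproduce. The check has two parts.

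**1. Guaranteed time, g, from the documents' windows**

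- Screening within 14 days before induction (protocol 5.2.2, consistent with 4.1 and 4.4): g up to about 14 days. Scheduled Selinexor starts on day 2 (protocol 3.1.2), which would make it 15. The optional baseline dose, if taken, shortens it.
- Screening up to 14 days before registration (Table 2) plus up to 14 days from enrolment to treatment (3.1): g up to 14 + 14 = 28 days.
- If on-treatment efficacy data means the first scheduled disease assessment, at the end of the 4-week cycle (protocol 5.1.1), add about 28 days: 14 + 28 = 42, or 28 + 28 = 56.

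**2. Effect on the estimates**

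Assumptions, none of them from the documents: exponential survival with true median m of 6 or 10 months, and 30.4375 days per month. Among patients alive at g, the median counted from consent is m + g. Survival at time t > g reads 2^(−(t − g)/m) instead of 2^(−t/m).

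- g = 14: 14/30.4375 = 0.46 months. 0.46/6 = +8%; 0.46/10 = +5%.
- g = 28: 28/30.4375 = 0.92 months. 0.92/6 = +15%; 0.92/10 = +9%.

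For m = 6 months (182.6 days), where true 6-month OS is 50.0%:

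| g (days) | Added to median (months) | 6-month OS reads | Expected deaths before qualifying, per 40 consented |
|---|---|---|---|
| 14 | 0.46 | 52.7% | 2.1 |
| 28 | 0.92 | 55.6% | 4.0 |
| 42 | 1.38 | 58.6% | 5.9 |
| 56 | 1.84 | 61.8% | 7.7 |

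The last column is 40 × (1 − 2^(−g/m)). Over a wider range of assumed medians, 14 days adds 15% at 3 months and 4% at 12 months.

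These figures give every patient the maximum gap. In a simulation with gaps spread evenly from 2 to 15 days (mean 8.5 days, or 0.28 months) and a true median of 6 months, the dosed patients' median was 6.23 months from consent and 5.96 months from first dose. For true medians of 3 and 12 months, the all-dosed analysis from first dose gave 2.98 and 12.10. Matching origin and set therefore removes the shift.

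**The case against.** The strongest reply is that the effect is small and may select nobody out. Patients had to be fit for 7+3 with ECOG of 2 or better, and the documents report no deaths before dosing. If there were none, counting from consent only moves the origin. That stands as a limit on the selection part. Each dosed patient's OS is still longer than OS from first dose by that patient's own gap.

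Size also counts against the point. At 50% survival with n = 40, the 95% half-width is about 1.96 × √(0.25/40) = 15 percentage points, against a shift of 2.7 points at 14 days. Protocol 8.4.1 makes all tests descriptive except that of the responder rate. Both facts stand, and they keep the point modest; a systematic shift is nevertheless not covered by a confidence interval.

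A reader might infer from Table 2 and protocol 3.1 that four weeks are guaranteed. The documents do not establish this. It requires both maximum windows to add, and protocol 5.2.2, 4.1 and 4.4 point to about 14 days. None of those three sections caps the consent date itself, so 28 days remains a possible upper bound.

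A reader might also infer that a patient must survive to the first marrow assessment to be counted. SAP 7.1 does not define on-treatment efficacy data. Early death rate is itself an efficacy variable tabulated on ITT, so an early death may qualify a patient, leaving no guaranteed time after the dose. The question is open and is left to the data review meeting.

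**Conclusion.** The mismatch is real, and nothing in the protocol, SAP or addendum corrects it. It builds in usually at most about 14 days of guaranteed survival. On assumed exponential medians of 6 to 10 months that is up to 0.46 months, or 8% down to 5%, and a 6-month OS of 50% would read about 53%. The 28-day figure (15% down to 9%) is an upper bound that depends on windows the protocol should reconcile. A further 28 days or so depends on an undefined phrase in SAP 7.1.

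A reader might infer that the trial's conclusion or a planned historical survival comparison is compromised. The documents do not support that. The primary response test and the sample size do not use these times, and no historical OS or RFS comparison is specified. The comparison of dosing schedules need not be biased either, if consent-to-dose gaps are similar. The result is a modest upward bias in descriptive secondary estimates, worth correcting because the correction is cheap.

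**What to change.** **OS.** In SAP 12.2, count OS from the date of first protocol treatment, using one rule for every patient. Analyse all patients who received at least one dose: the set in protocol 8.3.3, without the efficacy-data condition. The SAP's own safety set (7.3) should not be substituted, because it requires a later safety measurement. The rule must say whether the optional baseline Selinexor dose counts, and whether study medication includes the chemotherapy, so that the same event defines both date and set. Name this set for the OS tables and figures. Moving the origin while keeping the efficacy-data condition could still leave up to about 28 guaranteed days.

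**Sensitivity analysis.** Section 3 of the addendum shows that an initial analysis has already been run. The consent-based result should therefore be reported alongside, and the change declared as made after that analysis.

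**RFS.** State who is included. If all dosed patients, use the same origin and set as OS. If only responders, start at the date of CR/CRi; counting from first dose would still credit survival through one or two 4-week cycles. RFS would then coincide with what SAP 12.2 calls EFS, so the two definitions would need to be separated.

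**Windows.** Reconcile protocol Table 2 and section 3.1 with section 5.2.2, and report the observed consent-to-first-dose interval.

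**Cost.** Some SAP text and a few re-run tables and figures. Dose dates are in the CRF (protocol 6.2.3), and the addendum already requires survival to be recalculated. Medians will be slightly shorter.

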8.4.3 Efficacy Evaluation

Primary Efficacy Parameter

The primary efficacy measure will be the rate of complete responders (CR). Disease status will be assessed by bone marrow and peripheral blood analysis at the end of each 4-weeks induction and consolidation cycle. Disease status during maintenance will be evaluated by peripheral blood analysis at the end of each cycle and during follow-up after SCT every 3 months \pm 28 days. Bone marrow aspirate during maintenance and FU is required in case peripheral blood analysis is suspicious for progression of disease/relapse. Response is evaluated according to Döhner et al. criteria¹.

Secondary Efficacy Parameters

The secondary efficacy measures will be:

- Rate of partial remissions
- Percentage of patients being transplanted after induction therapy
- Early death rate
- Overall survival (OS)
- Event-free survival (Events are defined as Death, not achieving a CR or CRI, Relapse after CR or CRI)

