Secondary objectives of the study are 1) To determine the efficacy of Selinexor in combination with standard chemotherapy in patients with relapsed/ refractory AML by:

- Rate of partial remissions
- Percentage of patients being transplanted after induction therapy
- Early death rate
- Overall survival (OS)
- Event-free survival (Events are defined as Death, not achieving a CR or CRi, Relapse after CR or CRi) and

2) To evaluate overall safety and tolerability of Selinexor.

3 Design and type of the study

This is a phase II non-randomized, single-arm, open-label, multicentre study in patients with relapsed or refractory AML.

4 Study variables

The following variables will be evaluated.

The demographic and baseline variables:

Gender, age, race, details on leukemia diagnosis, prior therapy, medical history, current symptoms and residual toxicities from prior therapies, ECOG performance status, clinical neurological examination, cardiac evaluation, disease status, concomitant medication, prior transplantation, primary or secondary AML, early/late relapse from first therapy, mutation, karyotype risk category.

The primary efficacy variable:

The rate of complete responders according to the Cheson criteria.

The secondary efficacy variables:

Rate of partial remissions, percentage of patients being transplanted after induction therapy, early death rate, Overall survival (OS), Event-free survival (EFS), Recurrence-free-survival (RFS)

The safety variable:

Adverse events (AE), blood pressure, pulse, temperature, physical examination, urine analysis, hematology, clinical chemistry, coagulation tests.

5 Sample size considerations

The sample size calculation is based on the evaluation of response rates according to Fleming using the A'Hern extension (Sample size tables for exact single-stage phase II designs. Statist. Med. 2001;20:859-866). In Fleming's procedure to response levels p_0 and p_1 are specified, where p_0 is the largest proportion of responders, which would clearly imply that the treatment does not warrant further investigations and p_1 the minimum required proportion of responders that would imply that the treatment warrant further investigations. The following characteristics were specified in the sample size calculation:

- $p_0 = 0.30$
- $p_1 = 0.60$
- $\alpha = 0.05$ (one-tailed) and
- $\beta = 0.10$

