14.2.2 Secondary efficacy analysis

Table 14.2.2.1 Rate of partial remission overall and by dosing schedule (ITT)

Table 14.2.2.2 Rate of partial remission overall and by dosing schedule (PP)

Table 14.2.2.3 Percentage of patients being transplanted after induction therapy (ITT)

Table 14.2.2.4 Percentage of patients being transplanted after induction therapy (PP)

Table 14.2.2.5 Early death rate (ITT)

Table 14.2.2.6 Early death rate (PP)

Table 14.2.2.7 Summary statistics for overall survival endpoint (ITT)

Table 14.2.2.8 Summary statistics for overall survival endpoint (PP)

Table 14.2.2.9 Summary statistics for recurrence-free survival endpoint (ITT)

Table 14.2.2.10 Summary statistics for recurrence-free survival endpoint (PP)

Table 14.2.2.11 Summary statistics for event-free survival endpoint (ITT)

Table 14.2.2.12 Summary statistics for event-free survival endpoint (PP)

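### SAP 12.2 starts event-free survival at CR/CRi, so induction failures, which both documents count as events, cannot enter the analysis

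*SAP*

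**What the plan says.** The operative rule is in SAP 12.2: "EFS is calculated from the date of CR/CRi until death or relapse, whichever occurs first". The censoring rule follows: "Patients are censored on the date of last follow-up visit if they are alive without relapse". Neither sentence mentions patients who do not reach CR or CRi.

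The event definition elsewhere is different. SAP section 2 has "Events are defined as Death, not achieving a CR or CRi, Relapse after CR or CRi". Protocol 8.4.3 has "Events are defined as Death, not achieving a CR or CRI, Relapse after CR or CRI", and protocol 2.2 and the synopsis agree with it.

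SAP 12.2 gives the companion endpoint this rule: "RFS is calculated from the date of informed consent to the date of recurrence or death, whichever occurs first". RFS is not among the protocol's listed endpoints.

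The table and figure plan (SAP 19.2) labels the EFS curves ITT and gives the EFS summary tables for ITT and PP. Section 12.2 asks for curves in the overall population and by dosing schedule. The ITT set is not limited to responders: "The ITT set includes all subjects who have received study medication at least once and for whom efficacy data upon treatment are available".

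SAP section 15 declares one departure from the protocol, a clarification of the primary hypothesis. Section 3 of the 2018 addendum orders the relapse-free and event-free summaries and curves to be rerun but redefines neither endpoint.

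**The concern.** A clock that starts at remission cannot record failure to reach remission. One of the three event types named in the protocol and in SAP section 2 therefore disappears, together with deaths during induction. The patients who remain are selected for success, so the reported EFS is too favourable. It also says nothing about how many patients failed, because the result is the same whether 30% or 60% responded.

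RFS has the reverse problem. It starts at consent for everyone, including patients who never had a remission to lose, and recurrence is not defined for them. On the natural reading, a living non-responder is carried as recurrence-free.

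A reader of the ITT outputs would take a responder-only curve as the experience of the whole trial.

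**Working it through.** **The plan's own figure.** The documents give no EFS figure. The response rates used below come from the design in protocol 8.2: p0 = 0.30, p1 = 0.60, N = 25. That design reproduces. 25 × 0.30 + 1.645 × √(25 × 0.30 × 0.70) = 11.27, which rounds to 11, plus 1 = 12 responders. The exact one-sided alpha is 0.0442 and the power 0.922. The primary design is not affected by this point.

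**Which events the rule can record**

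| Event in protocol 8.4.3 and SAP 2 | Recorded under SAP 12.2? |
|---|---|
| Relapse after CR/CRi | Yes |
| Death after CR/CRi | Yes |
| Death before CR/CRi | No, the patient has no start date |
| Not achieving CR/CRi | No, the patient has no start date and it is not in the event list |

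**Patients without an EFS time.** The expected number is N × (1 − p), with N = 40 (protocol 3.2):
- p = 0.30: 40 × 0.70 = 28
- p = 0.40: 24
- p = 0.50: 20
- p = 0.60: 40 × 0.40 = 16

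If the 15 added patients are instead given their own planning rates of 65% or 70% (protocol 8.2) and the other 25 have 60%, the count is 10 + 5.25 or 10 + 4.5, so about 15. The range is then roughly 15 to 28 of 40.

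**Effect on the curve (illustration).** The following are assumptions, since the documents give none of them:
- Failures are events at t0, the end of cycle 1 or 2 (day 28 or 56, that is 0.92 or 1.84 months).
- Responders enter remission at t0.
- Time from remission to relapse or death is exponential with median m = 6 or 12 months.
- The clock starts at treatment.

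For t ≥ t0, EFS with failures counted is S(t) = p × 2^(−(t − t0)/m). The SAP quantity, measured from remission, is 2^(−t/m). For example, with m = 12, t0 = 1.84 and p = 0.30, S(12) = 0.30 × 2^(−10.16/12) = 0.30 × 0.556 = 0.167.

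| m (months) | p | 12-month EFS, failures counted (t0 = 0.92 / 1.84) | 12-month figure, SAP rule | Median, failures counted | Median, SAP rule |
|---|---|---|---|---|---|
| 6 | 0.30 | 8.3% / 9.3% | 25% | 0.9 / 1.8 | 6 |
| 6 | 0.60 | 16.7% / 18.6% | 25% | 2.5 / 3.4 | 6 |
| 12 | 0.30 | 15.8% / 16.7% | 50% | 0.9 / 1.8 | 12 |
| 12 | 0.60 | 31.6% / 33.4% | 50% | 4.1 / 5.0 | 12 |

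When p is 0.50 or less, the median with failures counted is t0, however long remissions last. Above 0.50 it is t0 + m × log2(p/0.5). For p = 0.60 and m = 12 that is t0 + 3.16.

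A simulation with responses at 1 or 2 months, failures at 2 months and m = 12 agrees. It gives 16%, 25% and 33% at response rates of 30%, 45% and 60%, against 50% under the SAP rule.

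**Different origins.** The table compares 12 months from treatment with 12 months from remission. This does not create the gap. On a common origin in the worked example, the responder-only value is 55.6% and the all-patient value is p times that, 16.7% at p = 0.30. Under these assumptions, leaving out the failures divides the true proportion by p.

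**The case against.** The contradiction itself is hard to dispute. The objections concern its reading and its weight.

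- **Exclusion is not written down.** The SAP never says that non-responders are left out, and it labels the outputs ITT. This is true; the exclusion follows from the missing start date. But 12.2 offers no other origin or event date, so no all-patient analysis can be run from it.
- **The measure is not pure remission duration.** Death also ends the interval, so it is relapse-free survival from remission. This stands.
- **The two endpoints are not simply swapped.** Only the start dates look exchanged. RFS as written omits induction failure, so exchanging the labels would not restore the protocol's EFS. This stands and shapes the fix. For RFS the safe statement is that it is undefined for patients who never remit.
- **The protocol gives no EFS origin or failure date.** The medians above therefore depend on dating failures at the end-of-induction assessment. That convention is an assumption, though a natural one: protocol 5.1.1 schedules marrow and blood at the end of each induction cycle.
- **EFS is secondary and descriptive.** No decision rule uses it. OS, response and early-death rates are reported separately, so induction failure is visible elsewhere. This limits the damage to the EFS and RFS results but does not make a responder-only curve under an ITT label correct.

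The SAP cites protocol version 2 rather than the current 3.1. That cannot explain the conflict, because SAP section 2 itself carries the three-event definition.

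**Conclusion.** The concern holds. SAP 12.2 contradicts both the protocol and SAP section 2, the change is not declared in section 15, and the addendum reruns the outputs without repairing the definition. Followed as written, EFS is computed in responders only and is biased upward.

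The firm part of the size is the count: 16 to 28 of 40 patients at response rates of 60% to 30% have no EFS time, and all of them would be events under the protocol's definition. The percentages are illustrative and rest on the assumed failure dates, exponential shape and remission medians. The gap at 12 months is about 17 to 34 percentage points for a 12-month median (50% against 33% to 16%) and about 6 to 17 points for a 6-month median (25% against 19% to 8%). The direction does not depend on those choices.

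The primary endpoint is unaffected. The definition must be corrected before any EFS or RFS result is reported.

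**What to change.** Replace the two definitions in SAP 12.2, or correct them in an addendum:

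- **EFS:** all treated patients, from the same origin as OS (informed consent in 12.2), to the earliest of induction failure, relapse after CR/CRi, or death. Induction failure means no CR or CRi at the end-of-induction assessment and is dated at that assessment.
- **RFS:** CR/CRi patients only, from the date of CR/CRi to relapse or death.

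Three clauses should go with this:
- Name the analysis set. All treated patients is wider than the ITT set, which also requires efficacy data and could drop early deaths.
- State how morphologic leukemia-free state is handled. The addendum counts it as response, but the EFS event definition names only CR and CRi, so under that definition these patients are induction failures.
- Say how a living patient with no end-of-induction assessment is treated.

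List the change in SAP section 15. Regenerate Figures 14.2.2, 14.2.3, 14.2.5 and 14.2.6, Tables 14.2.2.9 to 14.2.2.12, and Tables 14.2.3.2 and 14.2.3.3.

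The cost is a few sentences and a rerun that the addendum already orders in large part. No new data collection is needed for the failure dates, since the assessments are scheduled. The reported EFS will be less favourable.
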